The pQint-of-care PracTice to IMProve use of AnticoaguLation (OPTIMAL)-ACT trial is a prospective, randomized, investigator-initiated, trial to determine the optimal ACT target value in patients undergoing PCI. This will be the first prospective outcomes trial powered to identify the optimal ACT target range for reducing the rate of in-hospital bleeding (Bleeding Academic Research Consortium and EASY grading defined (Appendix I)). Different bleeding definitions will be used to account for shift in access site practice from femoral to radial, both here at Mayo Clinic Florida, and in the United States. In addition, the EASY grading scale is unique to transradial catheterization and complications related to bleeding may be more frequent among women (13). Rates of net adverse cardiovascular events (NACE) (defined as all-cause mortality, myocardial infarction (MI), stroke, or bleeding) would be identified as a primary safety endpoint in the trial. We aim to test the hypothesis that lower ACT target values, as compared to higher ACT target values, are associated with lower risk of bleeding without compromising efficacy as assessed by the primary safety endpoint. This finding would have significant implications for improving the safety of PCI by reducing bleeding complications.

**A. Significance:** The significance of the study proposal can be highlighted by 1) the recognition of the burden of coronary artery disease (CAD), 2) the widespread adoption and performance of PCI, and 3) the limited data regarding appropriate anticoagulation intensity during PCI. CAD causes 1 out of 6 deaths in the United States. Annually, over 600,000 patients suffer a coronary event, defined as a first hospitalized myocardial infarction or CAD-related death (14). Improvements in adherence to guideline-recommended therapies for patients with ischemic heart disease, including use of coronary revascularization procedures, have impacted the decline in deaths related to cardiovascular disease over the past several years. PCI is performed commonly in the United States with an estimated 490,000 procedures in 2010 alone (15). In patients with acute coronary syndromes, early revascularization with PCI has been

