Patients would be randomized to one of three ACT target groups (Figure 1). Patients will undergo randomization (1:1:1) to either low ACT target, medium ACT target, or high ACT target using a software automatic program (insert information on SDMS). ACT target ranges would be modified based on intended or provisional use of GP IIb/IIIa inhibitors. Target ranges for the OPTIMAL-ACT trial were based on both review of practice guideline recommendations, including the uncertainty expressed in the guidelines regarding ACT values and outcomes (4), and consensus agreement by study interventional cardiologists regarding clinical equipoise in the target ranges studied. PCI would be performed per routine clinical practice and selection of adjunctive oral antiplatelet therapies would be at the discretion of the operator and in accordance with clinical practice guidelines (4). Patients would be observed post PCI for

[figure not shown]
bleeding (primary endpoint), defined as BARC 1, 2,3 or 5 and EASY I-V (Appendix) and for NACE (i.e., ischemic events or bleeding as the primary safety endpoint). Follow-up would extend for 30-days post PCI for occurrence of the primary endpoint and primary safety endpoint. A dedicated telephone script will be used to contact the patient 30 days post-procedure. If the patient experienced a possible endpoint event and was treated at an outside facility, medical records will be obtained for review of whether the endpoint was met.

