#### F. Statistical Considerations:

**F1. Randomization and blinding:** Patients will be randomized (1:1:1) to one of the three ACT target groups (low, medium, or high) using a dynamic minimization algorithm so as to optimize the likelihood that balance between the low, medium, and high ACT target groups will be

achieved with respect to sex (male or female) and glomerular filtration rate (30 to 59 ml/min/1.73m^2 or ≥60 ml/min/1.73m^2). The algorithm will be implemented in RAVE RTSM, a secure web-based interface, and accessed by the study coordinator or other appointed study personnel. Randomization will be conducted after the diagnostic portion of the procedure on only patients who will require ACT monitoring. Since eligible patients will require ACT monitoring during PCI, we will not conduct the study in a strictly blinded fashion. However, study participants will not be informed of their randomization assignment.

**F2. Data collection and handling:** Electronic case report forms along with a corresponding secure REDCap database will be created for data collection (29). Data to be collected will include baseline demographics, comorbidities, procedural variables, in-hospital events, NACE component, and adverse events.

**F3: Definition of study outcomes:** Study endpoints are summarized in Appendix II.

**F3.1 Primary study endpoint:** Our **primary study endpoint is bleeding** and is defined as either a Bleeding Academic Research Consortium (BARC) hemorrhage grade of 1, 2, 3, or 5 or an EASY hematoma scale grade of I-V from the time of PCI to the time the patient is discharged from the hospital.

**F3.2 Primary safety endpoint:** Our **primary safety endpoint is a composite of net adverse clinical events (NACE) and stent thrombosis**, as defined by the Academic Research Consortium, from the time of PCI to the time the patient is discharged from the hospital.

**F3.2.1 NACE** is the composite of all-cause mortality, myocardial infarction (MI), stroke, target lesion revascularization, and major bleeding within 30 days after PCI.

**F3.2.2 MI** will be defined as any two of the following 3 criteria: 1) chest pain for at least 20 minutes; 2) elevation of cardiac biomarkers, preferably troponin, above the laboratory upper limit of normal; and 3) new pathological Q wave on electrocardiogram.

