**F3.3.3 Stroke** will have occurred if post-PCI neurological symptom is confirmed as a stroke by a consultant neurologist at Mayo Clinic with documentation on appropriate neuroimaging (CT or MRI).

**F3.3.4 Major bleeding** will be defined as BARC grade 3 or 5 or EASY grade ≥III.

**F3.3.5 Target vessel revascularization** will be defined as clinically driven revascularization, either by percutaneous or surgical means.

**F3.3.6 Intra-procedural events** would include both bleeding and thrombotic complications. Intra-procedural thrombus will be defined as a visible filling defect noted by the primary operator on the guiding catheter or intracoronary wire or device on selective angiogram.

**F3.4** The study definition of non-inferiority will be defined based on the 95% confidence interval for the difference in proportions of patients with NACE in the low and high ACT target groups,  $\Delta = p^L - p^H$ , with a lower limit of  $\Delta_L$  and an upper limit of  $\Delta_U$ . Low ACT target will be considered to be non-inferior to high ACT target if one of the following holds, depending on the estimate  $p^H$  :

- $\Delta_U < 0.12$  if  $p^H \geq 0.12$
- $\Delta_U < p^H$  if  $0.04 < p^H < 0.12$
- $\Delta_U < 0.04$  if  $p^H \leq 0.04$

Note that italicized version are the theoretical proportions and the estimates are not italicized.

**F.4. Sample size determination:** Recognizing the limitations of previously performed studies regarding ACT and risk of bleeding, including variability in definitions of bleeding, we estimate that the highest ACT target group will experience the in-hospital primary outcome at a rate of 25%, while the lowest ACT target will experience the in-hospital primary outcome at a rate of 5%. A **sample size of 504 patients** was determined to ensure more than 80% power at the

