## F5. Statistical analysis plans:

F5.1 Patient population for analysis: The primary analysis will include all randomized patients. Since patients will be randomized after the diagnostic portion of the procedure and the primary study outcome will be collected during their initial hospitalization after PCI, we anticipate negligible loss to follow-up and negligible imbalance between study arms. Analysis of the study aims will be conducted using an intent-to-treat approach, which means it will be an analysis including all randomized patients according to the group they were randomized regardless of whether or not the assigned ACT target was achieved.

F5.2 Primary analysis plan: Aim 1: The risk of in-hospital bleeding in the medium ACT target group and the high ACT target group will be compared to the risk of in-hospital bleeding in the low ACT target group using pair-wise chi-square tests (or Fisher's exact test). Relative risks and 95% confidence intervals will be reported. For these two tests of the primary study outcome, a two-sided p-value  $\leq 0.025$  will be considered statistically significant using the Bonferroni adjustment for multiple testing. This means that the overall two-sided level of significance for the trial will be 0.05. Aim 2: We will estimate the proportion of patients with each outcome (bleeding, NACE) along with 95% confidence intervals for the proportions using the Wilson score method separately for the three groups. Aim 3: We will create a 95% confidence interval for the difference in proportions of patients with NACE in the low and high ACT target groups using the Newcombe score method. This will be used to assess whether there is evidence of non-inferiority of low ACT target compared to high ACT target according to the definition in section F3.4.

F5.3 Secondary analysis plan: We will evaluate if associations between ACT target group (low, medium, high) and in-hospital bleeding are independent of sex, access site, and concomitant use of glycoprotein (GP) IIb/IIIa inhibitors (Aim 2) using a Cochran-Mantel-Haenszel test. For these pre-planned tests, a two-sided p-value  $\leq 0.0167$  will be considered statistically significant using a Bonferroni adjustment for multiple testing. Descriptive summaries and relative risks will be reported as in the primary analysis, except stratified by each of the patient or procedure characteristics.

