### EASY Hematoma Classification Scale

## Appendix II

### Optimal Target of Activated Clotting Time During Percutaneous Coronary Intervention and Outcomes: The OPTIMAL-ACT Trial

#### Study Endpoint Definitions:

##### Bleeding

-EASY hematoma classification after Transradial/Ulnar PCI

Type 1: less than 5cm in diameter from puncture site

Type 2: 5-10 cm in diameter from puncture site

Type 3: >10 cm in diameter but below the elbow limited to the forearm

Type 4:>10 cm in diameter and extends above the elbow

Type 5: any bleeding location with compartment syndrome (ischemic threat to the limb)

-BARC 2, 3, or 5 bleeding using BARC defined bleeding scale

BARC 0	No bleeding
BARC 1	Non-actionable bleeding
BARC 2	Actionable bleeding, even if on imaging alone, that meets one of the following:1) requires non-surgical (medical) intervention by healthcare personnel; 2) leads to hospitalization or escalation in level of care; 3) prompts evaluation.
BARC 3a	Overt bleeding AND hemoglobin drop 3 to 5 g/dL OR blood transfusion
BARC 3b	Overt bleeding AND hemoglobin drop $\geq 5$ OR cardiac tamponade, bleeding requiring surgical intervention for control, need for intravenous vasopressor
BARC 3c	Intracranial/intraspinal hemorrhage or intraocular hemorrhage with any visual impairment
BARC 4	CABG-related bleeding
BARC 5	Probable or definite fatal bleeding

Net Adverse Clinical Events (composite of all-cause mortality, myocardial infarction, stroke, target lesion revascularization, or bleeding)

Stent thrombosis (ST) :

Definite (ST): ACS with angiography or autopsy evidence of stent thrombosis.

Probable (ST): Unexplained death within 30 days of index procedure or acute myocardial infarction involving the target-vessel territory without angiographic confirmation.

Myocardial infarction: presence of 2 of the following: ischemic symptoms; elevation of cardiac troponin  $>99^{\text{th}}$  percentile of lab upper reference range with typical rise and fall; ECG changes compatible with infarction. For cardiac troponin elevated prior to PCI due to myocardial infarction, the subsequent troponin would need to be increased by 20% or more than the previous value to be considered an endpoint event.

Stroke: Focal loss of neurological function caused by an ischemic or hemorrhagic insult, with residual symptoms lasting at least 24 hours, and confirmed on neuroimaging (CT or MRI) with final impression deemed as stroke by a consulting neurologist

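### F3.4 sets its non-inferiority margin from the observed high-ACT NACE rate and ignores that rate's sampling error: error exceeds the implied 2.5% at true rates of about 3–11%, and the Aim 3 power claim is too broad

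*Combined protocol and SAP*

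**What the plan says.** Aim 3, a primary aim, tests non-inferiority of the low to the high ACT target on NACE.

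- **Rule (F3.4).** "Low ACT target will be considered to be non-inferior to high ACT target if one of the following holds, depending on the estimate" of the high-ACT proportion, pH. The upper 95% limit for pL − pH must be below 0.12 if pH is at least 0.12, below pH itself if pH lies between 0.04 and 0.12, and below 0.04 if pH is at most 0.04.
- **Interval (Aim 3 analysis in F5.2).** "We will create a 95% confidence interval for the difference in proportions of patients with NACE in the low and high ACT target groups", by the Newcombe score method. No allowance is made for a margin estimated from the same high-ACT patients, and no error level is stated for this aim.
- **Power (F.4).** More than 80% with 504 patients in three equal arms, if the arms truly have equal NACE and the high-ACT rate is 12% or above. The 12% is called a literature median, with range 4% to 20%. Table 2 reports only two NACE rates, 4% and 20%, so 12% is their midpoint: (4 + 20)/2.
- **Definition of NACE.** In F3.2.1 it "is the composite of all-cause mortality, myocardial infarction (MI), stroke, target lesion revascularization, and major bleeding within 30 days after PCI". The Rationale has it "defined as all-cause mortality, myocardial infarction (MI), stroke, or bleeding) would be identified as a primary safety endpoint in the trial", and Appendix II gives "Net Adverse Clinical Events (composite of all-cause mortality, myocardial infarction, stroke, target lesion revascularization, or bleeding"; neither limits bleeding to major bleeding. D. Approach also speaks of bleeding without that limit. F3.2 adds stent thrombosis and counts events, "as defined by the Academic Research Consortium, from the time of PCI to the time the patient is discharged from the hospital", whereas F3.2.1 uses 30 days.

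**The concern.** In the middle branch, one random quantity does two jobs. A high-ACT rate that is high by chance lowers the observed difference and widens the margin it is judged against. The Newcombe limit reflects only the first effect, so the rule passes too easily when the low target is truly worse by the full margin. In that branch, the full margin means twice the NACE rate.

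Aim 3 carries the trial's safety claim. If the true rate falls in the affected range, a non-inferiority statement would be read as having 2.5% error when the rule's own error is up to about three times that. The reader cannot tell from the plan whether the affected range applies, because the NACE definition is not settled.

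**Working it through.** **Inputs.** n = 504/3 = 168 per arm (F.4, equal allocation); two-sided 95% Newcombe interval (F5.2); margin rule from F3.4; no loss to follow-up (F5.1 calls it negligible). The 2.5% benchmark is inferred from the two-sided 95% interval.

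**Formulas.** With z = 1.96, the Wilson limits l and u for a proportion p are [p + z²/2n ± z√(p(1−p)/n + z²/4n²)]/(1 + z²/n). The Newcombe upper limit is U = (pL − pH) + √[(uL − pL)² + (pH − lH)²]. F3.4 passes if U < m, where m is pH confined to the range 0.04 to 0.12. All 169 × 169 outcomes were enumerated with exact binomial probabilities.

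**1. The plan's own figure (equal arms).**

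| True NACE rate | 4% | 8% | 12% | 15% | 18% | 19% | 20% | 25% |
|---|---|---|---|---|---|---|---|---|
| Power under F3.4 | 47.4% | 65.6% | 81.0% | 84.5% | 81.5% | 80.1% | 78.8% | 72.6% |

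The stated power is reproduced at 12% and holds to about 19%, but not for every higher rate.

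**2. Probability of declaring non-inferiority when the true difference equals the margin.**

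| True high-ACT rate | True low-ACT rate | F3.4 | Margin held at its true value |
|---|---|---|---|
| 2% | 6% | 2.44% | 2.13% |
| 3% | 7% | 4.18% | 2.32% |
| 4% | 8% | 7.39% | 2.36% |
| 5% | 10% | 7.50% | 2.37% |
| 6% | 12% | 7.78% | 2.48% |
| 7% | 14% | 7.98% | 2.56% |
| 8% | 16% | 7.92% | 2.54% |
| 9% | 18% | 7.26% | 2.50% |
| 10% | 20% | 5.80% | 2.58% |
| 11% | 22% | 4.01% | 2.53% |
| 12% | 24% | 2.49% | 2.55% |
| 15% | 27% | 2.61% | 2.61% |
| 20% | 32% | 2.62% | 2.62% |

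The last column isolates the cause: with the margin held fixed, the excess disappears.

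**3. Sample size.** In the middle branch the rule is in effect a test of pL − 2pH, whose variance is (vL + 4vH)/n, but it uses (vL + vH)/n. The large-sample error is 1 − Φ(1.96·√[(vL + vH)/(vL + 4vH)]), in which n cancels. At a high-ACT rate of 6%, vL = 0.12 × 0.88 = 0.1056 and vH = 0.06 × 0.94 = 0.0564. The ratio is 0.1620/0.3312 = 0.489, its square root is 0.699, 1.96 × 0.699 = 1.37, and the error is 8.5%. Exact values at rates of 4–9% with 252, 336 or 500 per arm are 7.7–8.5%. The sample-size re-estimation allowed in F5.5 therefore would not remove the excess.

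**4. One possible trial.** Take 17/168 (10.12%) in the low arm and 14/168 (8.33%) in the high arm. The Wilson upper limit for the low arm is 0.1561 and the lower limit for the high arm is 0.0503. U = 0.0179 + √(0.0549² + 0.0330²) = 0.0819, below the observed 0.0833, so F3.4 passes. The corresponding bound for pL − 2pH (MOVER, built from the same Wilson limits) is −0.0655 + √(0.0549² + 4 × 0.0330²) = +0.020. A doubling is not excluded.

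**5. Which rate applies.** F.4 says "we estimate that the highest ACT target group will experience the in-hospital primary outcome at a rate of 25" percent. If bleeding within NACE means that primary bleeding endpoint (an assumption), the high-ACT NACE rate is at least 25%. The margin is then in effect a fixed 0.12, and there is no excess. If only major bleeding counts, Table 2 shows major bleeding of 1–3%, and the NACE rate could fall in the affected range.

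**The case against.** The strongest reply is that the excess is absent at the plan's central assumption: 2.5% at a 12% rate. That stands.

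A reader might infer that every rate below 12% is affected. The documents do not support this. Below 4% a doubling lies inside the rule's own 0.04 floor, so accepting it is what the rule intends; tested at that floor, the error at a 2% rate is 2.4%.

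A reader might also infer that the major-bleeding definition in F3.2.1 puts NACE in the affected range. Table 2 does not show this. Its 20% NACE row has 1% major bleeding and 5% hematoma, so even if both counted, at least 20 − 1 − 5 = 14 points came from other components. F3.3.4 also counts EASY grade III or higher as major bleeding, and F3.2 adds stent thrombosis.

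The 7.3–8.0% applies at exactly a doubling and falls quickly beyond it. At a true 2.5-fold rate it is 2.4%, 1.9% and 1.2% for high-ACT rates of 4%, 6% and 8%; at threefold it is 0.7%, 0.4% and 0.1%.

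The 2.5% benchmark is an inference, and the power shortfall within the cited 4–20% range is only 80 − 78.8 = 1.2 points. Both are fair. Even so, the plan wrote branches for rates below 12%, cites 4% as the low end of its range, and gives no error rate for those branches.

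**Conclusion.** The concern holds in a limited range. With 168 per arm, F3.4 has error above the inferred 2.5% when the true high-ACT NACE rate is about 3–11%. The error is above 5% from about 3.5% to 10.25%, and is highest at about 8% for a true rate of 7%. There is no excess at about 2% or at 12% and above, and none if NACE counts any bleeding at the plan's 25% assumption. The documents do not establish which case will apply, so this is not a finding that the Aim 3 conclusion will be wrong. The power sentence in F.4 is wrong as written for rates above about 19%. These results assume 168 analysed per arm, the Newcombe interval as specified, and pH in F3.4 read as the estimate, as its wording says.

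**What to change.** Before any by-arm outcome comparison:

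1. Limit the Aim 3 power sentence in F.4 to NACE rates of about 12–19%, or replace it with a table of power by NACE rate.
2. State the intended Aim 3 error level and report the F3.4 error by NACE rate. A non-inferiority claim at an observed high-ACT rate of about 4–11% should not be reported as having 2.5% error.
3. Reconcile the NACE definition (major or any bleeding; with or without stent thrombosis and target lesion revascularization) and the window (discharge or 30 days), and say to which F3.4 applies.

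The cost is SAP wording and one table. No patients are added and the primary rule is unchanged.

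Optional, at the sponsor's choice:

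- **Sensitivity bound.** When the observed high-ACT rate is between 0.04 and 0.12, report the MOVER/Wilson upper bound for pL − 2pH. State the expected disagreement in advance: the bound fails where F3.4 passes in up to about 18% of trials with truly equal arms. It is not a required remedy. Combined with F3.4's 0.04 and 0.12 limits and applied at every observed rate, it would contradict F3.4 in 15.7% of equal-arm trials at a 12% rate, where there is no excess to correct, and its own error is 3.4% at a 4% rate.
- **One margin fixed in advance.** Error is then 2.3–2.6% at rates of 4–20%, but power depends on the margin, which is the sponsor's judgement. For illustration, 0.12 gives 91.6% power at a 12% rate but would accept a rise from 4% to 16%; 0.08 gives 61.0% at 12%.

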## F5. Statistical analysis plans:

F5.1 Patient population for analysis: The primary analysis will include all randomized patients. Since patients will be randomized after the diagnostic portion of the procedure and the primary study outcome will be collected during their initial hospitalization after PCI, we anticipate negligible loss to follow-up and negligible imbalance between study arms. Analysis of the study aims will be conducted using an intent-to-treat approach, which means it will be an analysis including all randomized patients according to the group they were randomized regardless of whether or not the assigned ACT target was achieved.

F5.2 Primary analysis plan: Aim 1: The risk of in-hospital bleeding in the medium ACT target group and the high ACT target group will be compared to the risk of in-hospital bleeding in the low ACT target group using pair-wise chi-square tests (or Fisher's exact test). Relative risks and 95% confidence intervals will be reported. For these two tests of the primary study outcome, a two-sided p-value  $\leq 0.025$  will be considered statistically significant using the Bonferroni adjustment for multiple testing. This means that the overall two-sided level of significance for the trial will be 0.05. Aim 2: We will estimate the proportion of patients with each outcome (bleeding, NACE) along with 95% confidence intervals for the proportions using the Wilson score method separately for the three groups. Aim 3: We will create a 95% confidence interval for the difference in proportions of patients with NACE in the low and high ACT target groups using the Newcombe score method. This will be used to assess whether there is evidence of non-inferiority of low ACT target compared to high ACT target according to the definition in section F3.4.

F5.3 Secondary analysis plan: We will evaluate if associations between ACT target group (low, medium, high) and in-hospital bleeding are independent of sex, access site, and concomitant use of glycoprotein (GP) IIb/IIIa inhibitors (Aim 2) using a Cochran-Mantel-Haenszel test. For these pre-planned tests, a two-sided p-value  $\leq 0.0167$  will be considered statistically significant using a Bonferroni adjustment for multiple testing. Descriptive summaries and relative risks will be reported as in the primary analysis, except stratified by each of the patient or procedure characteristics.

Baseline patient and procedure characteristics of the three groups will be reported as number and percentage for categorical variables and median and interquartile range for continuous variables. To evaluate the possibility of imbalance, we will make comparisons between the three randomized groups using a Kruskal-Wallis test for ordered or numeric variables and a chi-square test (or Fisher's exact test) for categorical variables. For those baseline characteristics with imbalance between groups, we will summarize the number and percentage as well as relative risk and 95% confidence intervals as was done with the pre-planned analyses of sex, access site, and concomitant use of glycoprotein (GP) IIb/IIIa inhibitors with stratification by the baseline characteristic. In addition, we will use a multivariable logistic regression model with in-hospital bleeding as our outcome measure and fixed effects for group (reference group = low ACT target), sex, access site, concomitant use of glycoprotein (GP) IIb/IIIa inhibitors, and any other baseline characteristics with evidence of potential imbalance between groups (p-value  $\leq 0.20$ ) allowing no more than one variable for every 10 patients who experience in-hospital bleeding.

F5.4 Exploratory analysis plan: We will explore the association of ACT target with individual components of bleeding and NACE using a Cochran-Armitage trend test and report the number and percent of patients with each component separately for each group. Adjustment for multiple testing will be conducted using the Holm step-down method.

F5.5 Interim analysis plan: A blinded review of the study's overall incidence of the primary study outcome and the primary safety endpoint will be planned after 50% of patients have completed the study. If this review suggests that assumed incidence used to plan the study is much higher than the actual event rate then we may reestimate the sample size to ensure the study is adequately powered. Since the analysis will be conducted blind to group assignment this will not introduce statistical bias and adjustment to the study's significance level is not required...

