two-sided overall 5% significance level with Bonferroni adjustment for multiple testing ( $p$  value  $\leq 0.025$  considered as statistically significant) to detect an absolute difference in in-hospital bleeding (Aim 1) between the low ACT target and the medium ACT target (ie. 5% vs. 15%) in addition to a 20% absolute difference between the low ACT target and the high ACT target (ie. 5% vs. 25%). The power was estimated on the basis of 5000 simulations. Patients meeting eligibility criteria for the study and who consent for participation but that do not undergo randomization due to either not receiving intracoronary diagnostic imaging (IVUS/OCT) or physiologic testing (iFR/FFR) or PCI will be entered into the ACT registry and observed for clinical events, including 30-day outcomes. The reason these patients are not categorized as screen failures is because the final criterion for eligibility is receipt of PCI, a criterion that is not known until the coronary angiogram is performed which is after patients have signed informed consent. Because patients receive moderate sedation during their procedure as part of standard of care, ethical and scientific prudence dictates that informed consent be obtained prior to procedural start. True screen failures, therefore, are those subjects not meeting study inclusion or exclusion criteria. . Based on current lab practice patterns at our institution, it is anticipated that approximately 20% of patients who enroll in the study will not require ACT monitoring after the diagnostic portion of the procedure, therefore we intend to consent up to 780 patients. In 2016, there were 240 PCI procedures and 220 adjunctive coronary imaging/physiology procedures (Fractional Flow Reserve = 158, Intravascular Ultrasound = 59, Optical Coherence Tomography = 12) establishing the feasibility of performing the study and meeting patient accrual targets over an **18 - 24 month period.**

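### The analyses that decide the trial use neither minimisation factor; stratifying them is a small, nearly free gain, and the open choice of Fisher's test should be closed

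*Combined protocol and SAP*

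**What the plan says.** F1 describes dynamic minimisation so that balance between the three arms is "achieved with respect to sex (male or female) and glomerular filtration rate" (30-59 vs 60 or more).

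F5.2 then sets the decision analyses:
- **Aim 1:** in-hospital bleeding in the medium and high arms "will be compared to the risk of in-hospital bleeding in the low ACT target group using pair-wise chi-square tests (or Fisher's exact test"), each at 0.025. "This means that the overall two-sided level of significance for the trial will be 0.05".
- **Aim 3:** 95% confidence limits are computed on this quantity: "difference in proportions of patients with NACE in the low and high ACT target groups using the Newcombe score method". They are read against the margin in F3.4.

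Neither analysis uses sex or GFR. F5.3 adds secondary bleeding analyses: Cochran-Mantel-Haenszel (CMH) tests by sex, access site and GP IIb/IIIa use, and a logistic model that always contains sex. GFR enters that model only if it passes an imbalance screen (p of 0.20 or less). No adjusted NACE analysis is planned.

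On prognosis, the introduction remarks that "complications related to bleeding may be more frequent among women", and Aim 4 (B.1.4) says the same of forearm bleeding after transradial procedures. No effect size is given. Nothing is said about GFR and bleeding, or about either factor and NACE.

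F.4 claims power above 80% from 5000 simulations without naming the test simulated. No rule is given for choosing Fisher over chi-square.

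**The concern.** Balancing arms on a prognostic factor removes that factor's contribution to the chance difference between arms. An unstratified test still counts it in its variance. The p-value is then somewhat too large and the interval somewhat too wide. Stratifying by the allocation factors corrects this with data already recorded at randomisation.

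GFR is the more exposed of the two factors. Minimisation makes it unlikely to fail the imbalance screen, so a factor important enough to balance on will probably enter no bleeding model. Neither factor informs the non-inferiority decision.

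The wording of the test raises a second, unrelated question. Pearson's test clears 80% power by only about one point, so the choice between Pearson and Fisher decides whether the F.4 claim is met.

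**Working it through.** **Inputs from the documents.** 504 patients, 168 per arm; bleeding 5% vs 15% and 5% vs 25%; two-sided alpha 0.025 per comparison (F.4, F5.2); NACE 12% in both arms with the F3.4 margin (F.4).

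**Assumed, because the documents give no figures.** 30% women, 25-30% with GFR 30-59, and the same odds ratio (OR) for each factor, from 1 to 3.

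**Step 1: reproduce the stated power, 5% vs 15%.** Normal approximation:

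power = Φ{[δ√n − z√(2p̄(1−p̄))] / √(p₁(1−p₁)+p₂(1−p₂))}

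= Φ{[0.10×12.961 − 2.2414×0.4243] / 0.4183} = Φ(0.825) = 79.5%.

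Exact enumeration of all 169×169 tables:

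| Test | 5% vs 15% | 5% vs 25% | Both |
|---|---|---|---|
| Pearson | 81.2% | 99.9% | 81.1% |
| Fisher | 76.4% | 99.9% | 76.4% |
| Continuity-corrected chi-square | 76.0% | 99.9% | 75.9% |

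The F.4 claim reproduces with Pearson only. Fisher first passes 80% at about 180 per arm (540 in total). Its actual size is 0.012-0.017, so its shortfall comes from discreteness and has nothing to do with sex or GFR.

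**Step 2: size of the unstratified test, in closed form.** If balance on the factors is complete, the true variance is the within-stratum part, a fraction r = 1 − V/[p(1−p)] of what the test assumes. V is the between-stratum variance of risk. Actual size ≈ 2Φ(−2.2414/√r).

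Take p = 0.15 and 30% prevalence for each factor, so the stratum weights are 0.49 (neither), 0.42 (one) and 0.09 (both).
- OR 3: risks 0.071, 0.187, 0.408. V = 0.49×0.0789² + 0.42×0.0368² + 0.09×0.2579² = 0.0096. r = 1 − 0.0096/0.1275 = 0.925. Size ≈ 2.0%.
- OR 2: risks 0.098, 0.178, 0.303. V = 0.0038, r = 0.971. Size ≈ 2.3%.

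Simulated minimised trials agree: 2.2-2.5% at OR 2 and 2.0-2.2% at OR 3, over bleeding rates of 10-15% (Monte Carlo SE about 0.1 point).

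**Step 3: Aim 1 power, 5% vs 15%, by simulation.** Unstratified chi-square vs CMH over the four sex by GFR strata:

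| OR per factor | 30% women, 25% low GFR | 30% women, 30% low GFR |
|---|---|---|
| 1 | 80.8-80.9 vs 80.6-80.7% | 81.1 vs 81.0% |
| 1.5 | 81.0-81.3 vs 81.1-81.3% | 81.5 vs 81.4% |
| 2 | 81.9-82.1 vs 82.4-82.5% | 81.3 vs 81.7% |
| 3 | 82.0-82.3 vs 83.5-83.6% | 82.3 vs 83.8% |

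The first column used 20,000 trials per setting, with minimisation probabilities of 0.8 and 1.0. With 20,000 trials the Monte Carlo SE of one power figure is √(0.82×0.18/20,000) = 0.27 point. Both tests are applied to the same simulated trials, so their differences are more precise than that.

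With only sex prognostic: 81.8 vs 81.8% (OR 1.5), 81.9 vs 82.0% (OR 2), 81.8 vs 82.4% (OR 3).

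**Step 4: Aim 3 at 12% NACE, both factors prognostic.** Non-inferiority power, unstratified Newcombe vs Mantel-Haenszel stratified risk difference:
- OR 1: 81.4 vs 82.2%
- OR 2: 81.7 vs 83.0%
- OR 3: 82.0 vs 83.9%

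The 0.8 point at OR 1 comes from the change of interval method. Net of that, stratification gives about 1.3 − 0.8 = 0.5 point at OR 2 and 1.9 − 0.8 = 1.1 points at OR 3. Newcombe coverage is 95.2%, 95.4% and 95.8%; Mantel-Haenszel coverage is 94.8%, 94.8% and 94.8%.

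The label stratified Newcombe covers more than one method. The Yan-Su form recovered essentially nothing (81.0 vs 80.8%, 81.5 vs 81.5% and 81.8 vs 81.9% at OR 1, 2 and 3). A variant built from stratified Wilson limits reached 82.5% at OR 2 and 83.9% at OR 3.

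**The case against.** An unadjusted primary test with an adjusted secondary model is a valid and conservative choice. The loss exists only if the factors are prognostic. The documents support that only qualitatively, for sex and forearm bleeding, and if sex alone matters the gain is about 0.1 point at OR 2 and 0.6 at OR 3. All of this stands, and it keeps the point small.

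A reader might infer that the planned tests are underpowered or invalid because they ignore the minimisation factors. The documents do not support that. Pearson's test exceeded 80% power in every Aim 1 setting simulated, and its error rate moves in the safe direction.

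A reader might also infer that the trial really has 76% power. That would hold only if Fisher were the test used. At the planned rates the pooled expectation is 168×0.10 = 16.8 events per arm. An expected count below 5 would need fewer than 10 events in the two arms together, which has probability about 1.5×10⁻⁷. A conventional small-count rule would therefore almost never select Fisher. What remains is that no rule is written down. Removing Fisher altogether would go too far, since F5.5 allows for event rates well below plan.

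**Conclusion.** The mismatch between allocation and analysis is in the text, and correcting it is a nearly free improvement. It does not rescue a failing design. The Aim 1 gain is nil at OR 1-1.5, about 0.5 point at OR 2 and about 1.5 points at OR 3. If neither factor matters, stratifying costs about 0.1-0.2 point. These figures rest on the assumed prevalences and equal odds ratios; the direction does not, provided a factor is prognostic.

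For Aim 3 the gain is of similar size but depends on the interval chosen, so a reader should not assume that any stratified interval recovers it.

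The Fisher point is separate and needs no covariate assumption. The F.4 statement holds for Pearson (81.2%) and fails for Fisher (76.4%) and for the continuity-corrected chi-square (76.0%), and F5.2 leaves the choice open.

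**What to change.** In F5.2:
1. **Aim 1:** make the two comparisons CMH tests stratified by sex by GFR class (four strata), without continuity correction, and report the Mantel-Haenszel relative risk with its interval. Keep crude proportions and relative risks as descriptive results.
2. **Aim 3:** name one stratified interval over the same strata, for example the Mantel-Haenszel risk difference with its variance estimator stated. Check its coverage by simulation before adopting it. State that the crude high-arm NACE proportion still selects the F3.4 margin.
3. **Choice of test:** name the uncorrected test as primary and allow Fisher only under a stated sparse-count condition, such as an expected cell count below 5. In F.4, name the test behind the power figure.

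The cost is SAP wording and a few lines of code, with no extra patients or data. The change should be made before any unblinded data are seen.
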